4.12 Outcome measures

Primary outcome measure:	Mortality (all causes) 30 days after randomisation.
Secondary outcome measures:	Mortality rate at first discharge from ICU Mortality rate at first discharge from hospital Mortality rate one year after randomisation Non-pulmonary organ failures whilst treated on an intensive care unit Health-related quality of life six months after randomisation Health-related quality of life one year after randomisation Pulmonary function one year after randomisation Ventilator-free days Antimicrobial-free days Sedative-free days
Primary health care system benefit:	Cost per quality-adjusted life year gained one year after randomisation
Secondary health care system benefits:	Intensive care unit length of stay Hospital length of stay Utilisation of hospital resources after acute hospital discharge one year after randomisation Utilisation of community care resources after acute hospital discharge one year after randomisation

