Your use of health and support services

If you are in your own home or are in a community-based care facility please complete section two.

If you are *not* at home or in community-based care you do not need to complete Section 2. Please go directly to Section 3 (page 18). Thank you.

This section of the questionnaire asks about health and support services you have **used** and anything you have had to **buy** since you left the Intensive Care Unit. We know that once patients have been discharged from hospital they may make use of other health and support services (for example, their family doctor, counselling, district nurse, or other hospital based services). This questionnaire asks you whether you have used any of these other health and support services, how often, and the costs to you (in terms of time and personal expenses). Your responses to these questions will give us a clearer idea of the actual costs involved.

When answering the following questions please think only about the time you were in the Intensive Care Unit **that led to you being entered in the OSCAR trial**. If you need help completing this section please ask someone to assist you who cares for

you and who knows which services and care you have had.

The information you give us will be confidential and will only used for the OSCAR study. Your answers will not affect any treatment you may be receiving now or any treatment you might receive in the future.

Please answer the questions that follow. Some questions will seem more relevant to you than others, but please try to answer all the questions.

Thank you.

Your use of primary and community based health and social services

32 Have you used any of the following services **since you left hospital** because of your stay in the Intensive Care Unit that led to your entry into the OSCAR study?

Have you visited/used any of these services:	In the last 6 months: Please tick (√) yes or no box on each line depending whether you physically attended a service	In last 6 months: Write the total number of face- to-face contacts for each service	In last 6 months: Write the total number of contacts by telephone or email for each service
a) GP, surgery visit	Yes No		
b) GP, home visit	Yes No		
c) District nurse	Yes No		
d) Health visitor	Yes No		
e) NHS Walk-in centre	Yes No		
f) Social worker	Yes No		
g) Physiotherapist	Yes No		
h) Occupational Therapist	Yes No		
i) Home help or care worker	Yes No		

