j) Citizens advice or welfare rights advisor	Yes No		
k) NHS Direct	Yes No		
 Lunch or social club organised by your local authority 	Yes No		
m) Food, medicine or laundry delivery service	Yes No		
n) Medical supplies	Yes No		
 Family or patient support or self help groups 	Yes No		
p) Respite care	Yes No		
q) Other (please specify):	Yes No		

Your use of hospital and residential care services

33 We would like to know whether you have used other hospital or residential care services since you were discharged from the hospital following your entry into the OSCAR study.

Have you used any of these services:		Since you left hospital: Please tick (√) 'yes' or 'no' box on each line depending whether you used a service	Since you left hospital: Give the total number of days you were in each service: Number of days:	Since you left hospital: Give total number of visits made to each service: Number of visits:
a.	Hospital inpatient stay	Yes No		
b.	Hospital day centre	Yes No		
C.	Hospital outpatient clinic	Yes No		
d.	Hospital accident and emergency visit	Yes No		
e.	Day centre run by your local authority	Yes No		
f.	Residential care home	Yes No		
g.	Rehabilitation centre	Yes No		
h.	Warden controlled residence	Yes No		

34 If you answered 'Yes' to using one or more of the services in question 33, please give us the name of the service and the area it is located in (see example in table below):

Type of service	Name of service used	Name of hospital/day centre/rehabilitation centre or care home	Town or city
Example: Hospital outpatient clinic	Back clinic	John Radcliffe Hospital	Oxford
a. Hospital inpatient stay			
b. Hospital day centre			
c. Hospital outpatient clinic			
d. Hospital accident and emergency visit			
e. Day centre run by your local authority			
f. Residential care home			
g. Rehabilitation centre			
h. Warden controlled residence			

Use of equipment and aids to help you after your stay in the Intensive Care Unit

35 Since you left hospital, have you used any special equipment or aids to help you (for example a toilet frame, a grab rail for your bed or a walking frame) due to your stay in the Intensive Care Unit that led to your entry into the OSCAR study?

36 If you answered 'yes' to question 35, who provided the equipment or aids following your stay in the Intensive Care Unit that led to your entry into the OSCAR study?

Provided by social services	Yes	No
Borrowed from friend/family	Yes	No
Bought by you	Yes	No

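### Question 32's tick column asks about physical attendance rather than use, so home-delivered or telephone-only care may be ticked as not used

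*Protocol*

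**What the plan says.** Section 4.12 of the Protocol lists, among the secondary health care system benefits, "Utilisation of community care resources after acute hospital discharge one year after randomisation". Section 4.13 says that the questionnaires sent to survivors at six months and one year include questions on social and health service use. The form is in Appendix 5.

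The introduction to Section Two of the form is about use: "This questionnaire asks you whether you have used any of these other health and support services". The stem of question 32 begins "Have you used any of the following services", and its row heading reads "Have you visited/used any of these services".

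The table has three answer columns:

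- The first is a "yes or no box on each line depending whether you physically attended a service".
- The second says "Write the total number of face- to-face contacts for each service".
- The third says "Write the total number of contacts by telephone or email for each service".

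The rows include a GP home visit, a home help or care worker, and "Food, medicine or laundry delivery service". Question 33, on hospital and residential care, has a tick column of the same layout, but its criterion is whether the service was used.

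**The concern.** The tick column measures something other than what the question and the outcome are about. Attendance means that the patient went somewhere. Some listed services work the other way round, and some contacts happen only by telephone or email. A respondent who follows the column heading closely could answer No for a service that was used, and could then take the count columns as not applicable.

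If that happens, the form shows no use where there was use, or shows a No beside a positive count. The affected data are the one-year community resource-use outcome and the costs that enter the economic analysis in section 4.14. Contacts that were never written down cannot be recovered by a later analysis rule, so the wording of the form matters in its own right.

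**Working it through.** No arithmetic in the protocol bears on this point, so the check is a reading of question 32 against its neighbours.

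**Step 1: the criterion in each place.**

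| Place | What it asks |
|---|---|
| Section 4.12, outcome | Utilisation |
| Section Two, introduction | Used |
| Question 32, stem | Used |
| Question 32, row heading | Visited or used |
| Question 32, tick column | Physically attended |
| Question 33, tick column | Used |

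The tick column of question 32 is the only one of the six that requires attendance. Question 33 mostly lists places, where attendance would have fitted better; question 32 lists several services that travel to the patient.

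**Step 2: what each reading of the tick column gives.** Attendance can be read literally (the patient went to the service) or loosely (in person rather than remotely).

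| How the service reached the patient | Literal reading | Loose reading | Use, as in question 33 | Count column available |
|---|---|---|---|---|
| Patient went to it | Yes | Yes | Yes | Face-to-face |
| Someone came to the patient | No | Yes | Yes | Face-to-face |
| Something was delivered | No | Unclear | Yes | Face-to-face, though not a natural unit |
| Telephone or email only | No | No | Yes | Telephone or email |

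Only the use criterion gives Yes in all four cases. Even the loose reading gives No for a service used only remotely, although the third column asks for exactly those contacts.

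**Step 3: when data are lost.** A contact is lost only if the respondent ticks No and, in addition, either leaves the count blank or has the count ignored in analysis because of the tick. The form tells nobody to skip the counts after a No, and the protocol does not say whether the tick or the count drives the costing. Loss is therefore possible but not established.

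**Step 4: size.** Let *h* be the share of contacts that are home-delivered or remote, and *r* the share of those contacts lost in the way just described. The share of all contacts lost is *h* × *r*. The protocol gives neither quantity, nor any contact rates. With *r* = 0 the loss is 0; otherwise the answer is whatever is assumed. The same holds for the contrast between arms: if a true difference *d* consisted wholly of such contacts and the same *r* applied in both arms, the recorded difference would be (1 − *r*) × *d*, so the shrinkage is simply the assumed *r*. No figure can be derived.

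**The case against.** The strongest reply is that the form already protects itself. The introduction, stem and row heading all speak of use. One row is explicitly a home visit, and a respondent who had one has little reason to tick No there. With a telephone and email column alongside, attendance reads naturally as meaning in person. A home visit is a face-to-face contact and can be entered as such whatever is ticked. Respondents are asked to try to answer everything, to seek help from someone who knows the care received, and to check Section Two for completeness. Question 33 also records some community services, such as local authority day centres. A rule on whether the tick or the count prevails would commonly sit in an analysis plan that is not shown, so its absence is no fault here.

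Most of this stands and limits the point to a risk. It does not remove the mismatch: the column still contradicts its own stem, and it still yields No for remote-only use under either reading.

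A reader might go further and infer that home care is answered No as a matter of course, that the loss is greatest in the most dependent survivors, and that the cost difference between arms is shrunk. The documents do not support that. Nothing shows that respondents leave counts blank after a No. That the least mobile use most home care is a reasonable supposition, but the protocol has no data on it. Both arms receive the same form, so a distorted contrast would need home-care use to differ by arm, and the protocol gives no evidence that it does. The analysis also takes an NHS perspective (section 4.14), and it is unclear whether home help or food and laundry delivery would enter the cost per QALY at all.

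**Conclusion.** The point holds as an inconsistency in the instrument with a real but unquantified risk. The tick column of question 32 conflicts with the question's stem and row heading, with question 33 and with the utilisation outcome in section 4.12. It fits badly at least three rows by their own labels (GP home visit, home help or care worker, delivery service) and any service contacted only remotely. Under-recording and mismatches between tick and count may follow if some respondents read the column literally and leave the counts blank, or if the analysis relies on the tick.

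Neither the size nor any effect on the comparison between arms can be calculated from the protocol. The affected results are the community resource-use outcome and, for services costed from an NHS perspective, the cost analysis. The primary outcome, 30-day mortality, is untouched. This is a modest point, worth correcting because the correction is cheap.

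**What to change.** For questionnaires still to be sent, bring the column into line with question 33, for example: *Tick yes or no on each line according to whether you used the service in any way: you went to it, someone came to you, something was delivered, or you had contact by telephone or email.* There is still time for this to help: the summary protocol in Appendix 9 has recruitment running to the end of July 2012, so one-year forms would fall due until about the end of July 2013.

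For forms already returned, take any face-to-face or telephone and email count above zero as use, whatever the tick. Do not recode a No with blank counts as unknown, because genuine non-users answer in exactly that way and would become missing data.

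The cost is one reworded column heading, notified to the ethics committee, and one derivation rule. The small downside is that the wording changes part-way through follow-up, though equally in both arms.

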Appendix 9: SUMMARY PROTOCOL FOR DOCTORS/NURSES

OSCAR Trial: Summary Protocol

MREC xxxx / Version 3 – 27 June 2011

The hypothesis

Patients with acute respiratory distress syndrome (ARDS) who are treated with high frequency oscillatory ventilation (HFOV) will have a decreased mortality at 30 days (post randomisation) compared with patients treated with conventional positive pressure ventilation.

The intervention and control groups

The study arms being compared in this trial are:

Group 1: High frequency oscillatory ventilation (HFOV) versus Group 2: Conventional positive pressure ventilation

The control group will receive conventional positive pressure ventilation using pressure-controlled artificial ventilation.

The intervention is high frequency oscillatory ventilation (HFOV) delivered using a Vision Alpha. The management of artificial ventilation with HFOV will be based on a simple algorithm .

Both groups will begin the treatment immediately following randomisation and the patients will remain on the ventilator until the start of weaning from artificial ventilation.

The setting

Ten or more ICUs in the NHS in the United Kingdom able to care for Level 3 patients as defined by "Comprehensive Critical Care".

Outcome measures

Primary outcome measure:	Mortality 30 days after randomisation.
Secondary outcome measures:	Mortality rate at first discharge from ICU Mortality rate at first discharge from hospital Mortality rate one year after randomisation Non-pulmonary organ failures whilst treated on an intensive care unit Health-related quality of life six months after randomisation Health-related quality of life one year after randomisation Pulmonary function one year after randomisation

Trial design

OSCAR is a multicentre, open, randomised controlled trial. This is a pragmatic, effectiveness study, where the mode of ventilation is determined randomly, but all other treatment decisions are left to the clinicians managing the patient.

Population to be studied

All adult intensive care patients requiring artificial ventilation who meet the inclusion criteria.

Eligible patients

Patients are eligible for the trial if they meet the following inclusion criteria:

Patients are eligible for the trial if they meet the following inclusion criteria:

- i. Age ≥16 years
- ii. Weight ≥35 kg
- iii. Receiving artificial ventilation via an endotracheal or tracheostomy tube
- iv. Have acute hypoxaemic respiratory failure as defined by:
 - ✓ Lowest recorded PaO₂/FiO₂ ratio measured between onset of artificial ventilation and time of screening of ≤ 26.7 kPa with a positive end expiratory pressure (PEEP) ≥ 5 cmH₂0
 - ✓ Bilateral infiltrates on chest radiograph
- v. Will not be extubated by tomorrow evening (predicted by attending clinician)
- vi. Have been mechanically ventilated for LESS than 7 consecutive days (≤ 168 hours) at the point of randomisation.

Clinical management of the 'high frequency oscillatory' ventilation arm

As HFOV will not have been used previously in most of the intensive care units in the study, before the study starts the clinicians in these units will be trained to operate the HFOV ventilator and follow the treatment algorithm.

Clinical management of the 'conventional' ventilation arm

The control patients will be managed using the current best conventional ventilation strategy, which is limited tidal volume, pressure controlled artificial ventilation.

Sample size

802 patients (401 in each arm).

Planned recruitment period

Recruitment started Dec 2007 and will continue until end July 2012.

For further information please contact the OSCAR Trial on: Email: [contact], [contact].

Appendix 10: FAMILY DOCTOR NOTIFICATION OF PATIENT IN TRIAL

UNIVERSITY OF OXFORD

[contact] [contact] Email: [contact]

> [Date] [address]

OSCAR Trial Office ICS Trials Group Kadoorie Centre for Critical Care [name] Patient's Trial Number: [xxxx]

Ref: MRECxxxx / V1/12 June 07

Dear Dr [name]

GENERAL PRACTITIONER NOTIFICATION OF PATIENT IN THE OSCAR TRIAL

This letter is to notify you that one of your patients has been recruited to the OSCAR Trial (Protocol Summary attached).

The patient concerned is:

[name]

Date of birth: [xx/xx/xxxx]

S/he was recruited to the study during their admission to the Intensive Care Unit (ICU) at the [hospital name] hospital in [month/year].

Whilst in the ICU, patients with the condition 'acute respiratory distress syndrome' (ARDS) are generally treated on a conventional artificial ventilator. The trial is comparing the use of a conventional ventilator with the use of a high frequency oscillatory ventilator for the treatment of ARDS. As your patient was diagnosed with the condition ARDS consent was obtained and they were entered into the trial.

We are notifying you of their participation in the research as they have now left the ICU. No action is required on your part.

Follow up of your patient

There are no further tests or hospital visits associated with the trial. We will however be contacting the patient by postal questionnaire at intervals of six months (up to 30 months post trial entry). We have obtained consent to do so. The questionnaire will ask how their breathing affects their day-to-day living, and a more generally about their wellbeing. If you would like a copy of the questionnaire please let us know.

We co-ordinate the UK study at the John Radcliffe Hospital and would be pleased to answer any questions you might have.

Yours sincerely,

[name] Chief Investigator OSCAR Trial Consultant in Adult Intensive Care

Enc: Protocol Summary

Appendix 11: POSTER FOR RELATIVES ROOM IN THE INTENSIVE CARE UNIT

(England/Wales/NI sample)

ISRCTN10416500 REC reference: 07/H0502/98 Version 2 - 3 September 07

OSCAR STUDY

This Intensive Care Unit (ICU) supports medical research to improve patient care and is currently involved in the national OSCAR Study, funded by the Health Technology Assessment Programme (a section of the Department of Health).

If the consultant in charge of the care of your relative, friend or person you are representing thinks that it is appropriate, you may be approached by a member of our ICU team to discuss their possible involvement in the OSCAR study.

It is likely that your relative, friend or person you are representing is not well enough to be able to decide for him/herself whether to participate. If this is the case, we will ask you to give your opinion as to whether you think they would have objected to taking part in this research.

The study has been approved by a Main Research Ethics Committee, and the Research and Development Department of this Trust.

If you would like any more information about the OSCAR study, please speak to a member of the ICU team.

Thank you.

OSCAR: WHY NOT IN TRIAL LOG

- -

ENGLAND/WALES REC ref: 07/H0502/98

- Version 1.3 / 12 June 07

Appendix 12

				The patient was not entered into the OSCAR trial because: (tick column that applies)							
				A	В	С	D	E	F	G	Н
No.	Today's date	Patient's date of birth	Sex (M/F)	Another trial patient is already on the Vision Alpha	Another non-trial patient is on the Vision Alpha	Oscillator not working/ technical failure	Patient has been ventilated for more than 7 consecutiv e days	Consultant predicts patient WILL be extubated by tomorrow evening	PERSONAL Consultee refused agreement	Nominated PROFESSI ONAL Consultee refused agreement	Other reason (Write reason below):
1											
2											
3											
4											

Brief details of patients considered for the trial but not entered will be recorded on this log at each collaborating unit. Recording this information is to establish an unbiased case selection and full reporting according to the CONSORT statement.

References (Nos. 64/65 in Protocol):

